2.6 Documentation and Other Considerations

All analyses will be conducted using SAS® software Version 9.4 or later.

3.0 Analysis of Baseline Subject Characteristics

Baseline and demographic characteristics will be summarized by treatment and overall for all subjects in the safety population. Age and baseline weight will be summarized with summary statistics. Gender, ethnicity, will be summarized with counts and percentages.

A detailed patient profile listing will be provided as shown in Appendix B. A detailed listing of demographic data for each subject will be provided as shown in Appendix B.

4.0 Analysis of Efficacy

4.1 Description of Efficacy Variables

4.1.1 Description of Primary Efficacy Variables

The following variables will be used to conduct the primary analysis of efficacy:

- Subject Global Impression assessments at Days 0, 8, 21, and 29;

4.1.2 Description of Secondary Efficacy Variables

The following variables will be secondary measures of efficacy:

- Motor Function Measure 20 (MFM-20, for Pediatric Subjects under 7 years) or Motor Function Measure 32 (MFM-32, for all other subjects). MFM-20 or MFM-32 Scores, depending on age, will be calculated as Totals for all items. MFM-20 and MFM-32 dimension scores are totals for item group D1 (Standing and Transfer), item group D2 (Axial and Proximal Motor Function), and item group D3 (Distal Motor Function). Additionally, these Motor Function Measure outcomes are also expressed as a percentage of the respective maximum possible total for all items and the three dimension groups, for both the MFM 20 and MFM 32. The percentages "normalize" the response between MFM 20 and MFM 32 so that

outcomes from these two groups of test subjects can be pooled for analysis across age groups;

- Clinical Global Impression-Severity;
- Clinical Global Impression-Improvement;
- Stimulated Single Fiber Electromyogram: mean jitter, median jitter, and percent block (this optional test is described in the protocol but not conducted at all trial sites);
- Slurp Test: Time (seconds) to make slurp sound (this optional test is described in the protocol but not conducted at all trial sites).

4.2 Analysis of Efficacy

4.2.1 Analysis of Primary Efficacy

Summary statistics for the SGI Day 0 assessment (baseline for period 1), SGI Day 8 assessment, and the corresponding change from baseline (CFB₁) will be presented by treatment and by treatment within mutation type (pre- vs. post-synaptic, see Table 2.2-1 above) as period 1. A Mann-Whitney-Wilcoxon test for equality of the CFB₁ in the two treatments in Period 1 will be presented. Summary statistics for the SGI Day 21 assessment (baseline for period 2), SGI Day 29 assessment, and the corresponding change from baseline (CFB₂) will also be presented by treatment and treatment within mutation type as period 2. Also, the change in CFB from Period 1 to Period 2 will be computed. This value estimates

$$\tau_1 - \tau_2$$

where τ_1 represents the treatment effect of the period 1 Investigational Product (IP) and τ_2 represents the treatment effect of period 2 IP. A Mann-Whitney-Wilcoxon test of the hypothesis that the above parameter is the same in both treatment sequences will be provided. Note that this is a nonparametric version of the treatment main effect in a linear model without carryover effects.

A mixed effects linear model will be fit to the data with SGI raw scores as the response. The model will include fixed effect terms for treatment, period, age group (2 to less than 6, 7 to less than 12, and 12 to less than 17 years of age, 17 years and over), mutation type and sequence*period, where sequence corresponds to the order in which the subject received treatments, and a random effect for subject. The LSMeans for the treatment groups will be calculated and provided, as will the estimated difference along with a 95% confidence interval for this difference and a formal hypothesis test that the difference in the means is 0.

Special care must be taken in crossover designs to ensure that there is not significant carryover effect; however, the pharmacological properties of amifampridine are such that

having a 12-day washout period should minimize any unequal carryover effects in the analysis.

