1.3 Sample Size

The primary analysis variable is the SGI Change from Baseline (CFB). It will be analyzed using the standard analysis for a two-by-two crossover design. The sample size required to control the power depends on the ratio of the between-treatment difference and the standard deviation of the difference (that is, the effect size). Assuming an effect size of 0.5, 23 patients per sequence will ensure power of 90% for the 2-sided test at the 0.05 level.

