A mixed effects linear model will be fit to each of the MFM datasets described above with percent outcome or individual item scores (as appropriate for each dataset) as the response variable. The model will include fixed effect terms for treatment, period, age group (2 to less than 6 years, 7 to less than 12 years, 12 to less than 17 years of age, and 17 years of age and above), genetic mutation type (see Table 2.2-1), and sequence*period, where sequence corresponds to the order in which the subject received treatments, and a random effect for subject. No carryover term will be fit. In the case of the MFM percent outcome datasets for the adult only patients, the age group fixed effect term will not be included in the model. The LSMeans for the treatment groups will be calculated and provided, as will the estimated difference along with a 95% confidence interval for this difference and a formal hypothesis test that difference in the means is 0. Note that it is highly likely that some specific mutations will have insufficient subjects to fit the specified model. In that case a notation will be made in the relevant table(s) that there are not sufficient observations to fit the model.

Special care must be taken in crossover designs to ensure that there is no significant carryover effect; however, the pharmacological properties of amifampridine (an elimination half-life of 1.8-2.5 hours) are such that having a 12-day restabilization period will minimize any unequal carryover effects in the analysis.

Clinical Global Impression

CGI-S and CGI-I will be summarized by frequency tables and percentages for each sequence group and period. The values will be analyzed with a Wilcoxon rank-sum test as outlined in Putt and Chinchilli (2004). The treatment effects will be estimated using the Hodges-Lehmann estimator and a 90% asymptotic confidence interval.

Single Fiber Electromyogram

Summary statistics for mean jitter, median jitter, and percent block will be presented by treatment and visit. No formal inferential procedures will be performed for these data.

Slurp Test

Summary statistics for the time to slurp sound from the slurp test and its CFB (Day 0 for Period 1 and Day 21 for Period 2) will be presented. No formal inferential procedures will be performed for these data.

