		Day 8	CFB	xxx	xxx	xxx	xxx	xxx	xxx
		Day 21 (Baseline)	RAW	xxx	xxx	xxx	xxx	xxx	xxx
		Day 29	RAW	xxx	xxx	xxx	xxx	xxx	xxx
		Day 29	CFB	xxx	xxx	xxx	xxx	xxx	xxx

^a RAW = observed data entered in the database; CFB = change from baseline = Score at time point - baseline score.
 STATKING Clinical Services (yyyy-mm-dd)
 Source Program: xxxxxxx.sas

Table format repeats for PP population.

Table 7. SGI Score Summary Mann-Whitney Main Effects Test Results
Catalyst Pharmaceuticals, Inc. - CMS-001
FAS Population (N=xxx)

Variable	Test	n	Mean Difference ^a	Test Statistic	P-Value
SGI	Period 1	xx	xxx	xxx	xxx
	Crossover	xx	xxx	xxx	xxx

^a The Period 1 mean-of-differences is the difference in mean CFB at the end of Study Period 1, corresponding to a parallel study design analysis. The Crossover mean-of-differences is the difference between the Period 1 CFB and Period 2 CFB.

STATKING Clinical Services (yyyy-mm-dd)

Source Program: xxxxxxx.sas

Table format repeats for PP population.

Page x of y

Table 9. SGI Score Mixed Model Analysis
Catalyst Pharmaceuticals, Inc. - CMS-001
FAS Population (N=xxx)

Statistic ^a	Amifampridine/ Placebo	Placebo/ Amifampridine
n	xxx	xxx
Least Squares (LS) Mean of Raw SGI Score	xxx	xxx
Between-Treatment Difference in LS Means (Amifampridine - Placebo)	xxx	
Denominator Degrees of freedom	x	
95% CI for Between-Treatment Difference in LS Means (Amifampridine - Placebo)	(xxx, xxx)	

^a Raw SGI score was modeled as the response, with fixed effects terms for treatment, period, age group, mutation type and sequence*period (i.e., carryover). Subject was treated as a random effect.

STATKING Clinical Services (yyyy-mm-dd)

Source Program: xxxxxxx.sas

Table format repeats for PP population.

Table 11. MFM-32 Score Summary Statistics by Treatment, Period and Time Point
 Catalyst Pharmaceuticals, Inc. - CMS-001
 FAS Population (N=xxx)

Treatment	Variable ^a	Period	Time Point	Data Type ^b	Std					
					Mean	Dev	n	Min	Max	Median
Amifampridine/Placebo	xxxxxxxx	1	Day 0 (Baseline)	RAW	xxx	xxx	xxx	xxx	xxx	xxx
			Day 8	RAW	xxx	xxx	xxx	xxx	xxx	xxx
				CFB	xxx	xxx	xxx	xxx	xxx	xxx
	xxxxxxxx	2	Day 21 (Baseline)	RAW	xxx	xxx	xxx	xxx	xxx	xxx
			Day 29	RAW	xxx	xxx	xxx	xxx	xxx	xxx
				CFB	xxx	xxx	xxx	xxx	xxx	xxx
Placebo/Amifampridine	xxxxxx	1	Day 0 (Baseline)	RAW	xxx	xxx	xxx	xxx	xxx	xxx
			Day 8	RAW	xxx	xxx	xxx	xxx	xxx	xxx
				CFB	xxx	xxx	xxx	xxx	xxx	xxx
	xxxxxx	2	Day 21 (Baseline)	RAW	xxx	xxx	xxx	xxx	xxx	xxx
			Day 29	RAW	xxx	xxx	xxx	xxx	xxx	xxx

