				CFB	xxx	xxx	xxx	xxx	xxx	xxx

^a This will correspond to one of the following: Dimension 1, 2, 3, the grand total, the corresponding percentages (X1, X2, X3, X), and the individual item scores.

^b RAW = observed data entered in the database; CFB = Change from baseline = Score at time point - baseline score.

STATKING Clinical Services (yyyy-mm-dd)

Source Program: xxxxxxxx.sas

Table format repeats for PP population.

Table 13. MFM-32 Score Summary Mann-Whitney Main Effects Test Results
 Catalyst Pharmaceuticals, Inc. - CMS-001
 FAS Population (N=xxx)

Scale	Test	n	Mean of Differences ^a	Test Statistic	P-Value
Total	Period 1	xx	xxx	xxx	xxx
	Crossover	xx	xxx	xxx	xxx
D-1	Period 1	xx	xxx	xxx	xxx
	Crossover	xx	xxx	xxx	xxx
D-2	Period 1	xx	xxx	xxx	xxx
	Crossover	xx	xxx	xxx	xxx
D-3	Period 1	xx	xxx	xxx	xxx
	Crossover	xx	xxx	xxx	xxx
Item xx	Period 1	xx	xxx	xxx	xxx
	Crossover	xx	xxx	xxx	xxx
Item yy	Period 1	xx	xxx	xxx	xxx
	Crossover	xx	xxx	xxx	xxx
Item zz	Period 1	xx	xxx	xxx	xxx
	Crossover	xx	xxx	xxx	xxx

^a The Period 1 mean-of-differences is the difference in mean CFB at the end of Study Period 1, corresponding to a parallel study design analysis. The Crossover mean-of-differences is the difference between the Period 1 CFB mean and Period 2 CFB mean. Individual items are sorted by the value of the test statistic associated with the crossover test.

STATKING Clinical Services (yyyy-mm-dd)

Source Program: xxxxxxx.sas

Table format repeats for PP population. Individual items will be ordered in increasing order of the p-values for the Crossover test.

Table 15. MFM-32 Score Mixed Model Analysis
 Catalyst Pharmaceuticals, Inc. - CMS-001
 FAS Population (N=xxxx)

Variable	Statistic ^a	Amifampridine/ Placebo	Placebo/ Amifampridine
Overall	n	xxx	xxx
	Least Squares (LS) Mean of Change from Baseline	xxx	xxx
	Between-Treatment Difference in LS Means (A-B)	xxx	
	Denominator degrees of freedom	x	
	95% CI for Between-Treatment Difference in LS Means (A-B)	(xxx, xxx)	
D1 Domain	n	xxx	xxx
	Least Squares (LS) Mean of Change from Baseline	xxx	xxx
	Between-Treatment Difference in LS Means (A-B)	xxx	
	Denominator degrees of freedom	x	
	95% CI for Between-Treatment Difference in LS Means (A-B)	(xxx, xxx)	
D2 Domain	n	xxx	xxx
	Least Squares (LS) Mean of Change from Baseline	xxx	xxx
	Between-Treatment Difference in LS Means (A-B)	xxx	
	Denominator degrees of freedom	x	
	95% CI for Between-Treatment Difference in LS Means (A-B)	(xxx, xxx)	
D3 Domain	n	xxx	xxx

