	Least Squares (LS) Mean of Change from Baseline	xxx	xxx
	Between-Treatment Difference in LS Means (A-B)	xxx	
	Denominator degrees of freedom	x	
	95% CI for Between-Treatment Difference in LS Means (A-B)	(xxx, xxx)	
Item xx	n	xxx	xxx
	Least Squares (LS) Mean of Change from Baseline	xxx	xxx
	Between-Treatment Difference in LS Means (A-B)	xxx	
	Denominator degrees of freedom	x	
	95% CI for Between-Treatment Difference in LS Means (A-B)	(xxx, xxx)	

^a Raw MFM score was modeled as the response, with fixed effects terms for treatment, period, age group, mutation type and sequence*period (i.e., carryover). Subject was treated as a random effect.

STATKING Clinical Services (yyyy-mm-dd)

Source Program: xxxxxxxx.sas

Table format repeats for PP population. Individual items will be ordered in increasing order of the p-values for the Crossover test.

Table 17. MFM-20 Score Mixed Model Analysis
 Catalyst Pharmaceuticals, Inc. - CMS-001
 FAS Population (N=xxxx)

Variable	Statistic ^a	Amifampridine/ Placebo	Placebo/ Amifampridine
Overall	n	xxx	xxx
	Least Squares (LS) Mean of Change from Baseline	xxx	xxx
	Between-Treatment Difference in LS Means (A-B)	xxx	
	Denominator degrees of freedom	x	
	95% CI for Between-Treatment Difference in LS Means (A-B)	(xxx, xxx)	
D1 Domain	n	xxx	xxx
	Least Squares (LS) Mean of Change from Baseline	xxx	xxx
	Between-Treatment Difference in LS Means (A-B)	xxx	
	Denominator degrees of freedom	x	
	95% CI for Between-Treatment Difference in LS Means (A-B)	(xxx, xxx)	
D2 Domain	n	xxx	xxx
	Least Squares (LS) Mean of Change from Baseline	xxx	xxx
	Between-Treatment Difference in LS Means (A-B)	xxx	
	Denominator degrees of freedom	x	
	95% CI for Between-Treatment Difference in LS Means (A-B)	(xxx, xxx)	
D3 Domain	n	xxx	xxx
	Least Squares (LS) Mean of Change from Baseline	xxx	xxx
	Between-Treatment Difference in LS Means (A-B)	xxx	
	Denominator degrees of freedom	x	
	95% CI for Between-Treatment Difference in LS Means (A-B)	(xxx, xxx)	
Item xx	n	xxx	xxx
	Least Squares (LS) Mean of Change from Baseline	xxx	xxx
	Between-Treatment Difference in LS Means (A-B)	xxx	
	Denominator degrees of freedom	x	
	95% CI for Between-Treatment Difference in LS Means (A-B)	(xxx, xxx)	

^a Raw MFM score was modeled as the response, with fixed effects terms for treatment, period, age group, mutation type and sequence*period (i.e., carryover). Subject was treated as a random effect.

STATKING Clinical Services (yyyy-mm-dd)

Source Program: xxxxxxxx.sas

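### The SAP mixed model fits treatment and sequence*period together, so the planned treatment difference and 95% CI for SGI and MFM cannot be estimated from one score per period; it also models raw score, not CFB

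*SAP*

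**What the plan says.** Protocol 15.7 makes the CFB in SGI the primary efficacy analysis, using the standard 2-by-2 crossover method; Protocol 15.8 does the same for standardised MFM scores. SAP 1.3 agrees on the endpoint: "The primary analysis variable is the SGI Change from Baseline (CFB"). SAP 4.1.1 lists as the primary variable "Subject Global Impression assessments at Days 0, 8, 21, and 29".

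SAP 4.2.1 gives two Mann-Whitney-Wilcoxon tests on CFB (period 1 alone, and the crossover comparison), then adds a model: "A mixed effects linear model will be fit to the data with SGI raw scores as the response". Its fixed effects are treatment, period, age group, "mutation type and sequence*period, where sequence corresponds to the order in which the subject received treatments, and a random effect for subject". The planned output is treatment LSMeans, their difference, a 95% CI and a test. SAP 4.2.2 repeats the structure for the MFM datasets and states: "No carryover term will be fit".

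In Appendix B the Table 9 footnote lists "fixed effects terms for treatment, period, age group, mutation type and sequence*period (i.e., carryover"). The MFM model footnotes describe the interaction in the same way. The Table 15 rows are labelled "Least Squares (LS) Mean of Change from Baseline", while its footnote says "Raw MFM score was modeled as the response".

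**The concern.** In a 2-by-2 crossover the sequence-by-period interaction and the treatment effect are the same contrast. A model that contains both cannot separate them, and neither covariates nor a random subject effect helps.

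What is at stake is the estimate. For SGI, Table 7 gives a mean difference, a test statistic and a p-value, but no CI. The mixed model is the only planned analysis that would give a treatment difference with an interval for SGI or MFM. It also supplies the T-score by which SAP 4.2.2 orders the MFM summaries. If software prints a number anyway, that number depends on column order or on an unstated visit coding.

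The raw-score response is a second departure. Protocol 15.6 says the SAP will note inconsistencies with the protocol; SAP 1.0 instead declares itself consistent and does not mention this one.

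**Working it through.** **Inputs.** Sequences AP and PA, 1:1, up to 23 subjects (SAP 1.1). Period baselines at Days 0 and 21; one post-treatment score per period, at Days 8 and 29 (SAP 4.2.1). Four age groups and pre- or post-synaptic mutation type (SAP 4.2.1); six mutations (SAP Table 2.2-1).

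**The plan's own figure.** The only related figure is the sample size: 23 per sequence for 90% power at effect size 0.5. For a crossover t test with N = 46, df = 44 and noncentrality 0.5 × √46 = 3.39, power is 91.3%; 22 per sequence gives 89.97%. The figure reproduces. It is power for the ordinary crossover contrast, which the mixed model below does not deliver. (Per sequence versus total enrolment is a separate matter; estimability does not depend on N.)

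**Step 1: the two terms coincide.** Code AP = +1, PA = −1; period 1 = +1, period 2 = −1; amifampridine = +1, placebo = −1.

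| Cell | sequence × period | treatment |
|---|---|---|
| AP, period 1 | +1 | +1 |
| AP, period 2 | −1 | −1 |
| PA, period 1 | −1 | −1 |
| PA, period 2 | +1 | +1 |

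**Step 2: rank of the fixed-effect design, one score per period.** The four cells give rank 4; four age groups add 3; two mutation types add 1 (six mutations add 5). So 4 + 3 + 1 = 8 and 4 + 3 + 5 = 12.

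| Terms | Rank with treatment | Rank without | A − P |
|---|---|---|---|
| treatment, period, sequence*period | 4 | 4 | not estimable |
| + age group, 2 mutation types (12/11) | 8 | 8 | not estimable |
| + age group, 6 mutations (12/11) | 12 | 12 | not estimable |
| sequence main effect instead of the interaction, basic | 4 | 3 | estimable |
| same, + age group, 2 mutation types | 8 | 7 | estimable |
| same, + age group, 6 mutations | 12 | 11 | estimable |
| interaction deleted, nothing added (age group, 2 types) | 7 | 6 | estimable |

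Keeping sequence*period and adding a sequence main effect beside it still gives 8 and 8. The random subject effect changes the covariance, not which fixed effects are estimable. In the basic model with a sequence main effect, the A − P weights on AP1, AP2, PA1, PA2 are +0.5, −0.5, −0.5, +0.5: the standard crossover contrast.

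**Step 3: stacking all four visits.** Keep treatment, period and sequence*period, and vary how the open-label baselines are coded.

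| Baseline coded as | Rank with / without treatment | Result |
|---|---|---|
| the period's randomised treatment | 4 / 4 | not estimable |
| amifampridine | 5 / 4 | estimable, but zero weight on both blinded-amifampridine cells |
| its own open-label level | 6 / 4 | +0.5 × (post − baseline) in AP1 and PA2, −0.5 × (post − baseline) in AP2 and PA1 |

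The third coding is the crossover CFB contrast. The second compares placebo with the preceding open-label score and ignores the blinded amifampridine results.

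**Step 4: what software might print.** If aliased columns are dropped, the treatment coefficient is PA2 − AP2 or AP1 − PA1, depending on which interaction column survives, or it is absent if the cells enter first. With assumed cell means, purely for illustration, of AP1 = 6.0, AP2 = 3.5, PA1 = 4.0, PA2 = 6.2:
- PA2 − AP2 = 6.2 − 3.5 = 2.7
- AP1 − PA1 = 6.0 − 4.0 = 2.0
- crossover contrast = 0.5 × (6.0 − 3.5) + 0.5 × (6.2 − 4.0) = 1.25 + 1.10 = 2.35

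The first two are between-group comparisons within one period; neither is the crossover estimate.

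**Step 5: the texts side by side.** Protocol 15.7 and SAP 1.3 name CFB; SAP 4.2.1 and Table 9 model raw SGI. Protocol 15.8 names CFB of standardised MFM; SAP 4.2.2 models percent outcome or item score. The MFM shells label their rows as CFB above footnotes that describe raw score (Tables 15, 17, 23, 25) or percent of maximum (Tables 27, 29, 31). SAP 4.2.2 rules out a carryover term for MFM, while the MFM footnotes call sequence*period carryover.

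**The case against.** The strongest reply is that the one-score-per-period reading is not stated. SAP 4.1.1 lists all four visits, Table 5 labels all four as raw, and Days 0 and 21 are scored on open-label drug. If those visits are a separate treatment level, the model as written returns exactly the crossover CFB contrast, and the raw-score objection largely goes too. That is true arithmetically. But no section gives that coding, Table 9 has only two columns, and the other two natural codings yield no estimate or the wrong one. An estimate that rests on an unstated coding is not prespecified.

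Second, neither document says that the mixed model is the decisive analysis, and SAP 4.2.1 does test CFB by rank methods. This stands: the p-value from the crossover rank test is safe. It does not supply an interval, and the SAP still needs to say which analysis decides.

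Third, some details vary. The model drops age group for adults, the footnotes of Tables 23, 27, 29 and 31 omit it, and those of Tables 27, 29 and 31 refer to percent of maximum. These points are correct but leave the aliasing intact, since every one of these footnotes keeps treatment, period and sequence*period.

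Fourth, deleting sequence*period alone would also restore estimability. That is right (rank 7 against 6); a sequence main effect is one valid repair, not the only one. The illustrative means say nothing about this trial; the rank result carries the argument.

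**Conclusion.** Wrong as written. With one post-treatment score per period, treatment adds zero degrees of freedom to a model that already contains sequence*period. The LSMean difference, its 95% CI and its test are then not estimable, for SGI and for every MFM dataset fitted with these terms. This is exact and does not depend on sample size, age grouping, mutation grouping or the random effect. With all four visits in the model, the result depends on a baseline coding that the SAP does not give, and only one of the three codings examined yields the intended contrast.

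The response conflicts with the endpoint named in Protocol 15.7, Protocol 15.8 and SAP 1.3, and the SAP does not flag it. The defect is confined to the mixed model: the period 1 and crossover Mann-Whitney tests on CFB, and the mean differences in Table 7, are unaffected. It must be fixed because the model is the only planned estimate with a CI for SGI and MFM.

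**What to change.** In SAP 4.2.1, SAP 4.2.2 and the mixed-model shells (Tables 9, 15, 17, 23, 25, 27, 29, 31 and their per-protocol repeats):

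1. Replace sequence*period with sequence as a main effect. Deleting the interaction outright is also workable.
2. Keep treatment, period, age group and mutation type where they apply, and random subject; make the footnotes list the same terms as the text.
3. Use period-specific CFB as the response: Day 8 minus Day 0, and Day 29 minus Day 21. Change the Table 9 row label and the MFM footnotes to match.
4. Delete the description of the term as carryover, so that the footnotes agree with SAP 4.2.2.
5. Head the LSMean columns by treatment; they are now headed by sequence although the row reports a treatment difference.
6. Reconcile Table 17, which the SAP 7.0 list calls an MFM-32 percent analysis and the shell calls an MFM-20 score analysis.

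Before unblinding, also state which SGI analysis is decisive, consistent with the protocol's standard 2-by-2 crossover analysis of CFB.

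The cost is one model statement, some SAP wording, and footnotes and labels. No new data are needed.
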